2.2.2 Baseline and change from baseline

Two baselines are defined:

- Baseline is the last available value prior to first administration of efgartigimod in the first cycle in 1705.
- CnB: Cycle n Baseline i.e. last available value prior to first administration of efgartigimod in cycle n, with n=1, 2, 3, etc..

Note: for MG-ADL and QMG, all assessments on the day of first administration of the IMP in cycle n are considered in the baseline selection, also those post-administration.

Change can be calculated from baseline or CnB. Note: baseline coincides with C1B. Baseline will be considered for analyses that assess across all cycles and the CnB will be used for analyses restricted to a specific cycle, n.

Change for safety parameters will be calculated from baseline only.

For efficacy and PD, a (percent) change can be calculated from baseline or CnB, according to the analysis.

	Statistical Analysis Plan	
ARGX-113-1705	Final Analysis	Final 1.0 of 20SEP2022

Change from baseline at time point t = value at time point t – baseline value.

Percent change from baseline at time point t = (actual value at time point t -baseline value)*100/baseline value.

Change from CnB at time point t = value at time point t – CnB value.

Percent change from CnB at time point t = (actual value at time point t - CnB value)*100/CnB value.

2.2.3 *Relative day*

Relative days in the period (ADYP) will be calculated according to the following rule:

- Concerned date < reference date: ADYP = concerned date – reference date
- Concerned date ≥ reference date: ADYP = concerned date – reference date + 1

The reference date is the date of first administration of study drug in the specific period, except for assessments in ITP0, for which the date of informed consent in 1705 will be taken as reference date.

2.2.4 *Analysis visits*

All assessments (from first ARGX-113-1705 cycle on), including unscheduled assessments, will be allocated to analysis windows. Tables and listings will present the analysis windows as defined below, not the CRF visits. Allocation of assessments will be done using their relative day in the period (see section 2.2.3).

Table 4: Analysis visits

Phase/Period	Analysis window	Target ADYP	Lower limit ADYP	Upper limit ADYP
Treatment/ cycle n (=Treatment Period n + ITP_n)				
	CnB	1	-INF	1*
	Week 1	8	1*	11
	Week 2	15	12	18
	Week 3	22	19	35
	Week 7	50	36	63
	Week 7 + (4*x)	50 + (x*28)	50 + (x*28) - 14	50 + (x*28) + 13

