4.2.2 Endpoint and derivation rules

1) Change and percent change (compared to Baseline and CnB) in total IgG level and IgG subtypes [IgG1, IgG2, IgG3 and IgG4] at each visit.

Analysis will be done by AChR-Ab status and overall.

2) Change and percent change (compared to Baseline and CnB) in anti-AChR antibodies (in AChR-Ab seropositive patients) at each visit.

See section 2.2.2 for calculation of change and percent change from baseline.

Values Below the limit of quantification (BLQ) will be imputed with the lower limit of quantification. Values Above the limit of quantification (ALQ) will be excluded from the statistical analysis and will thus also not be considered for the baseline selection. Patient with a baseline value BLQ will be excluded from the statistical analysis and only be listed.

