4.2.3 Statistical analysis

Summary statistics will be provided in terms of absolute values and changes from baseline and CnB for each treatment cycle. Moreover, percent changes from baseline and CnB will also be presented.

All data will be listed.

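### As worded, SAP 4.2.2 drops a patient with a BLQ baseline from the PD absolute-value summaries as well as from change and percent change; the exclusion should be limited to change statistics.

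*SAP*

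**What the plan says.** SAP 4.2.2 gives three rules for PD values outside the quantifiable range:

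- Low values: "Values Below the limit of quantification (BLQ) will be imputed with the lower limit of quantification".
- High values: "Values Above the limit of quantification (ALQ) will be excluded from the statistical analysis and will thus also not be considered for the baseline selection".
- Low baselines: "Patient with a baseline value BLQ will be excluded from the statistical analysis and only be listed".

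SAP 4.2.3 then sets out the analysis: "Summary statistics will be provided in terms of absolute values and changes from baseline and CnB for each treatment cycle". It adds percent changes from both references and a listing of all data. The planned tables include actual values for total IgG and its subtypes (14.2.3.1.1 and 14.2.3.1.2) and for anti-AChR antibodies in seropositive patients (14.2.3.3.1).

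On the reference value, SAP 2.2.2 states "Two baselines are defined". The first: "Baseline is the last available value prior to first administration of efgartigimod in the first cycle in 1705". The second is CnB, the last value before the first dose of cycle n. In percent change the reference is the denominator: "actual value at time point t -baseline value)*100/baseline value", with CnB substituted for the within-cycle version.

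**The concern.** A BLQ reference is a sound reason not to report change or percent change from it. It is no reason to discard that patient's measured levels, or changes in a later cycle whose own CnB is quantifiable. As written, the rule selects patients into the absolute-value tables by the level of the marker being summarised. A reader of a table labelled as the safety analysis set would not see that the lowest baselines had been taken out, or how many.

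The sentence also leaves three things open:

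- whether baseline means only the cycle 1 reference or also CnB;
- whether a BLQ baseline in one IgG subtype removes the patient from the other markers;
- whether the exclusion covers one cycle or all of them.

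Different programmers could resolve these differently.

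**Working it through.** **1. Scope of the exclusion.** Three textual points favour the wide reading.

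- The ALQ sentence excludes values; the BLQ-baseline sentence excludes the patient.
- Both sentences remove from the statistical analysis, and the section carrying that title (4.2.3) starts with absolute values.
- Nothing keeps the patient in tables 14.2.3.1.x or 14.2.3.3.1.

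**2. Where exclusion is justified.** With a BLQ reference set to the LLOQ and every later BLQ value also set to the LLOQ, the smallest possible percent change is (LLOQ − LLOQ) × 100 / LLOQ = 0. No fall can be shown, so change and percent change from that reference carry little information. Absolute values do not have this problem: the general rule ("will be imputed with the lower limit of quantification") is not limited to post-baseline values, so the baseline already has a usable figure.

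**3. Size.** There is no plan figure to reproduce: the documents give no LLOQ, ULOQ, BLQ share, PD mean or SD. All inputs here are assumptions: log-normal baseline with log-SD σ = 0.5, 1.0 or 1.5; share q BLQ; share a ALQ; z the standard normal quantile; Φ its distribution function. Ratios are to the true mean.

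- BLQ patients excluded: Φ(σ − z_q) / (1 − q)
- BLQ patients kept at the LLOQ: Φ(σ − z_q) + q · exp(σ z_q − σ²/2)
- BLQ and ALQ both dropped: [Φ(z_(1−a) − σ) − Φ(z_q − σ)] / (1 − q − a)

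Example with σ = 1 and q = 5% (z = −1.645):

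- Excluded: 0.9959 / 0.95 = 1.048, or +4.8%.
- Kept at the LLOQ: 0.9959 + 0.05 × 0.117 = 1.002, or +0.2%.
- With a = 5% as well: (0.7405 − 0.0041) / 0.90 = 0.818, or −18.2%.

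Ranges over the three values of σ, for the bias in the baseline mean:

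| BLQ share | Excluded | Kept at LLOQ | Excluded, plus 5% ALQ dropped |
|---|---|---|---|
| 1% | +0.8% to +1.0% | under +0.1% | −7% to −41% |
| 5% | +3.6% to +5.2% | +0.1% to +0.3% | −5% to −38% |
| 10% | +7.0% to +10.8% | +0.2% to +0.9% | −2% to −35% |
| 20% | +13.8% to +23.8% | +0.9% to +2.6% | +4.5% to −27% |

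A simulation of 2,000,000 draws agrees with the closed forms. It also gives the post-dose mean, assuming a log correlation of 0.8 with baseline and a geometric level 60% lower. Against keeping everyone at the LLOQ, exclusion raises that mean by 0.4-1% at 1% BLQ, 1-5% at 5%, 1-10% at 10% and 1-19% at 20%.

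For scale, SAP 1.3 gives a maximum of 167 patients, so 1%, 5% and 10% would be at most about 2, 8 and 17 patients. The anti-AChR tables use only the seropositive subset. With no BLQ baselines, every effect of this rule is zero.

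**The case against.** The other side has real weight.

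- **The rule may never apply.** Total IgG is unlikely to be BLQ, and anti-AChR is summarised only in seropositive patients. The first treatment period needs an MG-ADL total of at least 5 with less than 2 points of improvement (Protocol 4.1), and IgG in healthy volunteers was back at baseline about 8 weeks after the last dose (Protocol 1.2). Both point to few depleted baselines, though neither rules them out.
- **The author may have meant only change statistics.** SAP 4.2.2 names only change and percent change as endpoints, and the protocol endpoint (3.3) is a percentage decrease, for which excluding a BLQ reference is right.
- **Little depends on it.** The trial is described as essentially descriptive (Protocol 8), and all PD data are listed.

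These points hold down the priority. They do not settle the scope, because 4.2.3 puts absolute values under the analysis from which the patient is excluded, and a listing does not correct a summary table.

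A reader might also infer stronger things that the documents do not support:

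- **That the tables do overstate levels.** No BLQ count is given, and the ALQ rule pulls the other way.
- **That a BLQ CnB in a later cycle is kept and used as denominator.** The word baseline in 4.2.2 can be read as covering CnB or as the cycle 1 reference only.
- **That one BLQ marker removes the patient from all PD markers.** The sentence does not say so.
- **That the former-efgartigimod and former-placebo columns are affected unequally.** Their entry levels could differ, but no figures are given.

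**Conclusion.** The point holds as a conditional one. On its wording, SAP 4.2.2 removes BLQ-baseline patients from absolute values and later cycles without need. Where such patients exist, that rule alone pushes the absolute summaries up: about 1% in the baseline mean at 1% BLQ, 4-5% at 5% and 7-11% at 10%. These sizes rest on assumed log-normal baselines and assumed BLQ shares. Low-level IgG subtypes and anti-AChR are the plausible exposure, and total IgG probably has none. The net direction of the reported levels is not established, since dropping ALQ values can outweigh the effect. The protocol's percentage-decrease endpoint is not harmed by excluding a BLQ reference as such. This is a low-priority clarification for tertiary, descriptive, Part A summaries.

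**What to change.** Replace the last sentence of the BLQ/ALQ paragraph in SAP 4.2.2 with:

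*For each PD parameter, change and percent change are not calculated relative to a reference value (Baseline, or the CnB of that cycle) that is BLQ. The patient's absolute values, and changes relative to a quantifiable reference, stay in the summaries with BLQ set to the LLOQ. The numbers of BLQ and ALQ values are shown per group, cycle and visit.*

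This settles which reference, which parameter and which statistics are meant, and the counts show whether the issue arose at all. The cost is one sentence, a filter on the change variables and added count rows. There are two small downsides. Absolute means will include some LLOQ-imputed values, with a residual bias of at most about 0.3% at 5% BLQ and 0.9% at 10% under the assumptions above. The ALQ exclusion also remains, so if ALQ values occur the low tail is kept while the high tail is still dropped; the ALQ counts make that visible.

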4.2.3 Statistical analysis

Summary statistics will be provided in terms of absolute values and changes from baseline and CnB for each treatment cycle. Moreover, percent changes from baseline and CnB will also be presented.

All data will be listed.

4.3 ANTI-DRUG ANTIBODIES

4.3.1 Available data

During part A of the study, presence of anti-drug antibodies (ADA) to efgartigimod is measured at the roll-over visit, at baseline and week 3 of each cycle and at EoA.

During part B, ADA is measured at baseline and EoS only.

[figure not shown]
ADA samples are analysed in a 3-tiered approach:

- All samples are evaluated in the ADA screening assay and are scored ADA screening positive or negative.
- If a sample scored ADA screening positive, it is further evaluated in the confirmatory assay and is scored confirmed positive (positive immunodepletion) or confirmed negative (negative immunodepletion).
- If a sample is scored as confirmed positive, the samples are further characterized in the ADA titration assay (to determine titer) and are also further analysed in the Nab assay to confirm neutralizing activity (positive or negative).

If available, a titer result will be reported for the ADA confirmed positive samples. However, a titer result is not always available:

- In case the ADA confirmed positive sample could not be run in the titration assay (e.g. due to insufficient sample volume/quality to perform the titer analysis) the result will be described as ‘positive immuno-depletion’ and the sample should be considered as ADA positive.
- If a sample is negative in the titration assay, it will be reported as ‘negative titer’ but the sample should be considered as 'ADA positive' since it was confirmed positive in the second tier.
- If a sample is not reported or reported as ‘positive screen’, the ADA sample status is ADA unevaluable.

An overview of this 3-tiered approach and all possible ADA sample results that will be reported by the laboratory is given below. From these reported ADA sample results a final ADA sample status needs to be derived during the statistical analysis, as presented in the final column (Final ADA Outcome):

^a Missing screen includes the following terms (reported as reason not done): NA (not analysed), NR (no result), NS (no sample) and SL (sample lost). More details can be found in the IS data transfer agreement from SGS France to SGS SD office.

^b 'positive titer' is reported in case it was not possible to retrieve a numeric value.

4.3.2 Derivation rules

4.3.2.1 SUBJECT CLASSIFICATION FOR ADA – OVERALL AND BY CYCLE

Table below gives an overview of how the ADA subject classification will be derived, starting from the patient baseline ADA sample status.

Subject ADA classification	Highest ^c post-baseline ^d sample status				
	ADA negative	ADA positive (missing titer ^a)	ADA positive (negative titer ^b or numeric titer value)		ADA not evaluable
Baseline ADA sample status					
ADA negative	ADA negative	Treatment Induced ADA	Treatment Induced ADA		ADA unevaluable
ADA positive (missing titer ^a)	Treatment Unaffected ADA	ADA unevaluable	ADA unevaluable		ADA unevaluable
ADA positive (negative titer ^b or numeric titer value)	Treatment Unaffected ADA	ADA unevaluable	titer < 4 x baseline titer: Treatment Unaffected ADA	titer ≥ 4x baseline titer: Treatment Boosted ADA ^e	ADA unevaluable
ADA not evaluable	ADA unevaluable	ADA unevaluable	ADA unevaluable		ADA unevaluable

^c Samples with missing titer have as reported ADA result 'positive immunodepletion' or 'positive titer';
^d Results reported as 'negative titer', i.e. titer value <1 will be set to value of 1;
^e Highest sample status, with order: (from low to high): ADA unevaluable, ADA negative, ADA positive (missing titer /positive immunodepletion), ADA positive with titer < 1 ('negative titer' as reported ADA result, titer value set to 1), ADA positive with titer ≥ 1 (i.e. positive titer and selecting the sample with highest titer)
^f For the overall ADA subject classification, the highest post baseline sample status over all cycles is used for comparison with the baseline ADA sample status.
 For the cycle ADA subject classification, the highest post baseline sample status within the cycle is used for comparison with the baseline ADA sample status.
^g Note: Four-fold difference in titer values is considered significant in case a twofold serial dilution is applied (=two times the dilution factor) (reference to Shankar et al., 2014).

ADA evaluable patient = patient classified as any of following categories: ADA negative, treatment unaffected ADA, treatment induced ADA, treatment boosted ADA.

ADA unevaluable patient = patient classified as unevaluable or with missing baseline ADA sample or without post-baseline ADA samples.

In case no ADA data is available at all, the participant cannot be classified.

ADA incidence = percentage of patients with treatment-induced or treatment-boosted ADAs (denominator: number of evaluable patients). Treatment-unaffected ADAs are not taken into account.

ADA prevalence = percentage of patients with treatment-unaffected ADA, treatment-induced ADA or treatment-boosted ADA (denominator: number of evaluable patients).

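### By-cycle ADA incidence counts a persistent treatment-emergent ADA again in each later cycle, so it shows prevalence of treatment-emergent ADA rather than new onset

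*SAP*

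**What the plan says.** SAP 2.2.2 defines two reference values. The first is study baseline: "Baseline is the last available value prior to first administration of efgartigimod in the first cycle in 1705". The second is CnB: "Cycle n Baseline i.e. last available value prior to first administration of efgartigimod in cycle n".

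SAP 4.3.2.1 builds the ADA subject classification "starting from the patient baseline ADA sample status". Its footnote then gives two rules. For the overall classification, "the highest post baseline sample status over all cycles is used for comparison with the baseline ADA sample status". For the cycle classification, "the highest post baseline sample status within the cycle is used for comparison with the baseline ADA sample status". The reference phrase is the same in both, and CnB is not named.

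The same section sets the rates: "ADA incidence = percentage of patients with treatment-induced or treatment-boosted ADAs", over evaluable patients. Prevalence adds the treatment-unaffected category. SAP 4.3.3 tabulates both rates by cycle and overall, using the category of the applicable cycle, and table 14.2.4.2 displays them. SAP 4.3.2.2 classifies NAb with the same reference wording, but its incidence sums two categories: baseline negative to post-baseline positive, and baseline positive to post-baseline positive.

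ADA incidence and prevalence is a tertiary endpoint for Parts A and B (protocol 3.3). The protocol synopsis plans ADA tables by cycle and overall.

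**The concern.** In a re-treatment trial, a reader will take a by-cycle incidence to answer whether new ADA arise as cycles accumulate. Under the footnote, each cycle is compared with the same pre-cycle-1 sample, so a patient who has converted and stays positive returns to the numerator each time. A flat series could be read as steady new immunisation when all conversions happened in cycle 1. A rising series could come from attrition alone, since SAP 2.2.1 expects patient numbers to decline over cycles. If nobody is positive at study baseline, the treatment-unaffected category is empty, and the table prints by-cycle incidence and prevalence as the same number.

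**Working it through.** The documents give no ADA rate, so there is no planned figure to reproduce. The check applies the SAP's own rules to assumed data.

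**Rules (SAP 4.3.2.1).** Negative to positive = induced. Positive to a titer at least 4 times baseline = boosted. Positive to a lower multiple, or to negative = unaffected.

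- Incidence = (induced + boosted) / evaluable.
- Prevalence = (induced + boosted + unaffected) / evaluable.
- First onset in cycle k = patients first induced or boosted in cycle k / evaluable patients not induced or boosted in an earlier cycle.

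**Assumptions.** 100 evaluable patients, five cycles, no attrition, stable titers after conversion, study baseline as reference.

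| Assumed pattern | Plan's by-cycle incidence, cycles 1 to 5 | First onset, cycles 1 to 5 |
|---|---|---|
| 10 convert in cycle 1 and persist | 10, 10, 10, 10, 10% | 10/100 = 10%, then 0/90 = 0% |
| 10 as above, plus 2 boosted in cycle 1 and persisting | 12, 12, 12, 12, 12% | 12/100 = 12%, then 0/88 = 0% |
| 10 in cycle 1, plus 3 in cycle 3, all persist | 10, 10, 13, 13, 13% | 10%, 0%, 3/90 = 3.3%, 0/87, 0/87 |
| 10 convert in cycle 1, negative in all later cycles | 10, 0, 0, 0, 0% | 10%, then 0% |

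In the first pattern, 10 conversions give 5 × 10 = 50 patient-cycle counts. With 5 persistent converters it is 5% in every cycle (25 counts for 5 conversions). With 20 it is 20% in every cycle (100 for 20). Overall incidence in the first pattern is 10/100 = 10%, because each patient is classified once over all cycles.

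**Attrition.** Assume 150 evaluable patients in cycle 1 (SAP 1.3 gives a maximum of 167 enrolled) and 75 in a late cycle, with no new conversions. If all 10 persistent positives remain, the plan's figure goes from 10/150 = 6.7% to 10/75 = 13.3%. If 5 remain, it is 5/75 = 6.7%. Neither late figure describes onset.

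**Whether CnB would be a better reference.** Two checks against the same classification table:

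- A patient induced in cycle 1 with a stable titer is positive at C2B with a ratio below 4, so cycle 2 becomes treatment-unaffected although the drug induced the antibody.
- Take a study-baseline titer of 1 and then 2, 4, 8 in successive cycles. Against study baseline the ratios are 2, 4, 8, so the patient is boosted from the second of these cycles. Against CnB each ratio is 2, so the patient is never boosted.

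**NAb.** Assume 5 of 100 patients convert in cycle 1 and persist. Against study baseline they are negative-to-positive in every cycle: 5/100 = 5%. Against CnB they are negative-to-positive in cycle 1 and positive-to-positive afterwards. Both categories count as incident, so the result is again 5% in every cycle. Changing the reference changes nothing.

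**The case against.** The strongest defence is that incidence is explicitly defined as induced plus boosted, not as new in that cycle, and that comparison with study baseline is a legitimate way to show treatment-emergent ADA. That stands, and it is why the classification should be kept. What remains wrong is the label, and the absence of any row showing onset.

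A reader might infer more than the documents support:

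- **That the SAP breaks its own rule.** SAP 2.2.2 does say that "the CnB will be used for analyses restricted to a specific cycle, n", and its only stated exception concerns safety parameters. But the sentence stands in a section on change from baseline and does not name ADA, while 4.3.2.1 is a specific categorical rule. This is an unexplained choice, not a demonstrated contradiction.
- **That the reference is beyond doubt.** SAP 4.3.1 uses the word baseline loosely: for Part B it can only mean cycle baseline. The defined term in 2.2.2 and the single phrase used for overall and by-cycle classification favour study baseline, but the footnote should say so.
- **That the table cannot show new ADA.** It can in part: in the third pattern, the rise from 10% to 13% is visible. By-visit ADA status (table 14.2.4.1) and the patient listing 16.2.12.1 are also planned.
- **That CnB is the remedy.** It would label drug-induced ADA as unaffected and lose gradual boosting, as shown above.
- **That NAb has the same cause.** It does not: its incidence definition counts any evaluable patient with a post-baseline positive.

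**Conclusion.** The point holds for by-cycle ADA incidence, read on the SAP's defined terms. The planned row is the prevalence of treatment-emergent ADA within the cycle. The number of repeat counts depends on persistence: none if ADA are transient, and up to the full cycle 1 figure repeated in every later cycle if all persist. Attrition can move the figure either way. Every rate above is an assumption, and *every later cycle* means every later cycle with an evaluable positive sample.

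Overall ADA incidence is unaffected. The endpoint is tertiary and, under protocol section 8, evaluation is essentially descriptive, so no inferential conclusion is at risk. The matter should be corrected because it is cheap and decides what table 14.2.4.2 can be used for. For NAb the incidence definition itself needs changing.

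**What to change.** 1. State in the 4.3.2.1 footnote that the reference for the cycle classification is study baseline, and keep the classification as it is.
2. In table 14.2.4.2, relabel the present by-cycle incidence as prevalence of treatment-emergent ADA in the cycle.
3. Add one row per cycle for first onset: patients first classified as induced or boosted in that cycle, over evaluable patients not already induced or boosted in an earlier cycle. Label it as first onset in 1705, since patients who received efgartigimod in 1704 were not drug-naive at this baseline.
4. In 4.3.2.2, remove the category positive at baseline and positive afterwards from NAb incidence. Persistent negative-to-positive patients would still repeat by cycle, so add a first-onset row for the first change from baseline-negative to post-baseline-positive.

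No new samples are needed. The cost is SAP wording and one extra row per cycle. Late-cycle first-onset percentages will rest on small denominators, so show numerator and denominator beside each.
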